10.3.2. Analysis Populations

All enrolled Patients will be included in the analysis. Patients who have had bilateral PAAs treated with the GORE® VIABAHN® Endoprosthesis in both limbs will have only the data from the first limb collected in this study when the limbs were treated at different dates. Patients that had PAAs treated in both limbs on the same date will be excluded to avoid confounding issues with select endpoints.

10.3.3. Pooling of Data

CONFIDENTIAL INFORMATION

Data from all study Sites will be pooled on a clinical basis, i.e., the study Sites will follow a common protocol, the study will be monitored to assure compliance with the protocol and applicable government regulations, and the data collection and handling procedures will be the same at all study Sites.

10.3.4. Primary Endpoints

Performance will be evaluated by primary patency at 12 months of the GORE® VIABAHN® Endoprosthesis in the treatment of Popliteal Artery Aneurysms. A point estimate will be calculated requiring primary patency at the one year visit to be declared a success. Having loss of primary patency at day 365 will be tabulated as a failure. Primary patency is defined in section 3.3.1.

Safety of the GORE® VIABAHN® Endoprosthesis will be assessed through 12 months by evaluation of serious adverse events (SAEs) and adverse events related to the study procedure or the study device. Counts will be tabulated at 12 months.

10.3.5. Secondary Endpoint(s)

Primary patency, which is defined as blood flow maintained through the device without an intervention. Blood flow should be determined at the follow-up visits, by either angiography or color-coded duplex sonography. In the event that duplex sonography is not obtained, blood flow will be assessed by clinician exam. Primary patency at 12, 24, & 36 months after implant will be estimated through time-to-event analysis.

Serious adverse events and adverse events relative to the study device and procedure will be obtained through 36 months for assessment of the device safety. Counts will be tabled at 24, & 36 months.

Length of hospital stay will be measured in calendar days. Length of hospital stay will be calculated omitting all patients with unknown endpoint status.

Length of procedure will be measured in minutes. Length of procedure will be calculated omitting all patients with unknown endpoint status.

Primary assisted patency at 12, 24, & 36 months after implant will be estimated through time-to-event analysis. Blood flow should be determined by angiography or color-coded duplex sonography. In the event that duplex sonography is not obtained, blood flow will be assessed by clinician exam.

Freedom from limb loss of the study limb at 12, 24, & 36 months after implant will be estimated through time-to-event analysis.

Freedom from repeat intervention at 12, 24, & 36 months after implant will be estimated through time-to-event analysis.

Secondary patency at 12, 24, & 36 months after implant will be estimated through time-to-event analysis. Blood flow should be determined by angiography or color-coded duplex sonography. In the event that duplex sonography is not obtained, blood flow will be assessed by clinician exam.

Technical Success

Technical success is defined as successful aneurysmal exclusion using the GORE® VIABAHN® Endoprosthesis at time of the procedure without Type I and III endoleaks that require post-procedure intervention within 30 days. All subjects without known status for this endpoint will be omitted in calculating this statistic.

CONFIDENTIAL INFORMATION

MD133246 Protocol Template

Revision#: 1

Doc Type: GC

Additional listings

In addition, listings of the following events will be provided: endoleak, migration, fracture, and amputation.

10.4. Control of Bias

Bias will be controlled by strict adherence to patient eligibility criteria and to the study protocol. Sites will be monitored for compliance with study protocol, including subject eligibility criteria, and will be audited for both compliance with the protocol and for data quality.

10.5. Data Analysis

Analysis will be performed after all of the data has been obtained, entered, cleaned, and locked for the interim as well as the final analyses.

11. Ethical and Regulatory Considerations

11.1. Statement of Compliance

The study will be conducted in compliance with this protocol, International Conference on ISO 14155, and applicable regulatory requirements (see **Table 5** below).

Table 5. Applicable Regulations for this Clinical Study.

ICH-GCP E6	International Conference on Harmonisation Regulations Guideline For Good Clinical Practice
ISO 14155:2011	Clinical investigation of medical devices for human patients – Good clinical practice
Medical Device Directive (93/42/EEC) Article 15 Annex X	Council Directive 93/42/EEC of 14 June 1992
Amendment to the MDD (2007/47/EC) Article 15 Annex X	Directive 2007/47/EC of the European Parliament and of the Council of 5 September 2007

11.2. Compliance Responsibilities

The Sponsor will conduct the clinical study in accordance with all applicable regulations and laws. The Sponsor will be responsible for documenting that Investigators have the necessary skills, training, and information to properly conduct the clinical study. The Sponsor will ensure proper monitoring of the clinical study and ensure appropriate approvals were obtained prior to enrollment. The Sponsor will provide information to the Investigators concerning the progress of the clinical study and any new, material information about the clinical study.

The Investigator will conduct the clinical study in accordance with all applicable regulations and laws, any relevant agreements, the study protocol, and all approval conditions of the reviewing Committees. The Investigator is responsible for protecting the rights, safety, and welfare of patients under his / her care.

11.3. Informed Consent

CONFIDENTIAL INFORMATION

It is the responsibility of the Investigator to give each patient prior to inclusion in the investigation, full and adequate verbal and written information about the objectives of the study. The patients must be informed about their right to withdraw from the investigation at any time and for any reason without sanction, penalty or loss of benefits to which they are otherwise entitled and that withdrawal from the investigation will not jeopardize their future medical care. Written Patient Information should be given to each patient before enrolment.

In compliance with national regulatory requirements, the Patient Information Sheet and Informed Consent Form will be submitted to the CCTIRS and to CNIL to be compliant with their requirements. The Investigator will provide the original copy of the signed and dated informed consent to the subject and a copy will be maintained in the subject's medical record. In addition, the signed and dated informed consent will be reviewed by the clinical monitor during the monitoring visit to ensure that it is properly executed in compliance with regulation. The Investigator, or his / her designee, must document in the subject's medical record that informed consent was obtained prior to study participation.

If applicable the Informed Consent will be updated or amended whenever new information becomes available that may be relevant to the patient and the patient advised of this information and re-consented. All modifications to the Informed Consent template must be approved by Gore prior to any submission and use.

11.4. Conflict of Interest

All Investigators will follow their Site's conflict of interest policies.

11.5. Confidentiality

This research is subject to the law of January 6, 1978 relating to Data Protection, as amended and will be submitted to the French Advisory Committee on Information Processing in Material Research in the Field of Health (CCTIRS), and then the French Data Protection Agency (CNIL) before its actual commencement.

All subject records will be kept confidential to the extent provided by applicable laws and regulations. The study monitors and other authorized representatives of the Sponsor may inspect all documents and records required to be maintained by the Investigator, including but not limited to medical records.

Such records may also be reviewed by other regulatory bodies.

The Investigator will inform the patients that their records may be reviewed.

**CONFIDENTIAL INFORMATION**

## 1.0 Introduction

This Statistical Analysis Plan (SAP) describes the statistical analyses planned to address the objectives of FPR 14-03. This SAP summarizes the analyses that will be performed to determine the safety and effectiveness of the GORE® VIABAHN® Endoprosthesis when used for the treatment of subjects with Popliteal Artery Aneurysms. This SAP outlines tables, figures, and listings that are included in reports for the FPR 14-03 clinical study.

## 2.0 Study Design Overview

### 2.1 Objectives

#### 2.1.1 Primary Objectives

The primary objectives of the GORE® VIABAHN® Endoprosthesis Popliteal Artery Aneurysm study are to document the safety and performance of the GORE® VIABAHN® Endoprosthesis for the treatment of PAAs at 12 months.

#### 2.1.2 Secondary Objectives

The secondary objectives of the GORE® VIABAHN® Endoprosthesis Popliteal Artery Aneurysm study are to document long-term (through 36 months) safety and performance by evaluating freedom from limb loss, length of hospital stay after study procedure, length of study procedure, serious adverse events (SAEs), device or procedure related adverse events (AEs), technical success, primary patency, primary assisted patency, secondary patency and freedom repeat intervention. In addition, listings of device migration, endoleak, device fracture, and study limb amputation will be reported separately.

### 2.2 Design Summary

This is a retrospective, multicenter, non-randomized single-arm clinical study with a prospective follow-up to evaluate the safety and performance of the GORE® VIABAHN® Endoprosthesis for the treatment of patients with PAAs. All patients will have received the GORE® VIABAHN® Endoprosthesis for treatment of a PAA since September 15, 2012 (date at which reimbursement for the GORE® VIABAHN® device was received in France). Inclusion for all patients will be retrospective, follow-up visit(s) can be prospective.

A maximum of 10 Clinical Investigative Sites (referred to as "Sites" in the remainder of this document) in France will participate in this study. 50 patients with an adequate follow-up to assess primary endpoints will be enrolled. All patients will have received the GORE® VIABAHN® Endoprosthesis for treatment of a PAA since 15 September 2012 and meet all of the inclusion and none of the exclusion criteria as specified in Sections 4.2 and 4.3 of this protocol.

Data entry will be monitored and enrollment will be stopped when 50 subjects have data for the 12 months follow-up visit entered.

Patients with bilateral PAAs treated with GORE® VIABAHN® Endoprosthesis at different dates can be enrolled in the study. The first limb enrolled will be considered the study limb. Patients with both limbs treated within the same procedure will not be enrolled in the study.

Follow-up examinations through 12 months (+/- 3 months) post-implant will be collected for the primary endpoint analysis. This will include clinical assessment, imaging-based

evaluations, SAEs, device, and procedure related AEs. Patients will be further followed through 24 and 36 months post-procedure.

## 2.3 Study Endpoints

### 2.3.1 Primary Endpoints

#### 2.3.1.1 Primary Patency at 12 Months

The primary performance endpoint for this trial is primary patency at 12 months. Primary patency is defined as blood flow without occlusion maintained through the device after implant without an intervention.

#### 2.3.1.2 Primary Safety

The primary safety endpoint for this trial are serious adverse events and adverse events related to the study procedure or the study device at 12 months. An adverse event is any untoward medical occurrences, unintended disease or injury or any untoward clinical signs (including abnormal laboratory findings) in patients, users or other persons related to the investigational medical device or procedure. For this study, only device or procedure related adverse events need to be reported. A serious adverse event is an adverse event that led to death or lead to serious deterioration in the health of the subject that resulted in a life threatening illness or injury, or a permanent impairment of a body structure of body function, or in-patient or prolonged hospitalization, or a medical or surgical intervention to prevent life-threatening illness or injury, or permanent impairment to a body structure or a body function.

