3.3. Study Endpoints

3.3.1. Definitions

Acute Limb Ischemia[55]: Defined by the operating or treating physician. Typically defined as emergently threatened, whether marginally or immediately, implying reversible ischemia in a limb that is salvageable without a major amputation if arterial obstruction is relieved quickly or irreversible ischemic change requiring major amputation.

Adverse Event (AE): Any untoward medical occurrences, unintended disease or injury or any untoward clinical signs (including abnormal laboratory findings) in patients, users or other persons related to the investigational medical device or procedure.[56] For this study, only device or procedure related AEs need to be reported.

Device Fracture: A stent fracture was defined as any discontinuity of the normal structure of the stent as diagnosed on x-ray.

Endoleak (Modified from White et al.)[57]:

Type I – Present when a persistent perigraft channel of blood flow develops due to inadequate or ineffective seal at the graft ends.

Type II – Occurs when there is persistent collateral blood flow into the aneurysm sac flowing retrogradely from collateral branches.

Type III – Arises at the mid-graft region due to leakage through a defect in the graft fabric or between the segments of multiple grafts.

Type IV –Blood diffusion across the pores of the graft fabric or through tiny holes in the graft fabric caused by sutures or stent struts.

Type V - Leakage from an unknown origin.

Hinge Point: Located at the adductor tubercle, which corresponds to the upper border of the patella, in a plane perpendicular to the femoral axis.

Length of Hospital Stay: The number of days the subject remains in the hospital due to endovascular repair of a PAA with VIABAHN (“index procedure”).

Length of Procedure: The number of minutes the subject remains in the operating room or catheterization laboratory due to endovascular repair of a PAA. If no specific information is available the first and last angiographic timestamp can be used to capture the length of the procedure.

Limb Loss: An amputation on the study limb above the metatarsals.

Migration: Any post-operative device migration requiring treatment.

Patency:

Primary Patency: Blood flow without occlusion maintained through the device after implant without an intervention.

Primary Assisted Patency: Blood flow maintained through the device after implant regardless of re-interventions performed (without occlusion).

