Secondary Patency: Blood flow through the device regardless of re-interventions performed (with or without occlusion) and freedom from surgical bypass.

Re-intervention: Endovascular or surgical procedure performed to treat a stenosis or occlusion within the study device(s) or within 5 mm of the proximal or distal edge of the device(s), treatment of endoleaks or other reasons.

Serious Adverse Event (SAE)[56]: An AE that led to death or lead to serious deterioration in the health of the subject that resulted in a life threatening illness or injury, or a permanent impairment of a body structure of body function, or in-patient or prolonged hospitalization, or a medical or surgical intervention to prevent life-threatening illness or injury, or permanent impairment to a body structure or a body function.

Technical Success: Successful aneurysmal exclusion using the GORE® VIABAHN® Endoprosthesis at time of the procedure without Type I or III endoleaks that require post-procedure intervention within 30 days.

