8.4. Risk-to-Benefit Rationale

CONFIDENTIAL INFORMATION

MD133246 Protocol Template
Revision#: 1
Doc Type: GC

This study does not lead to any change in patient management and patients will receive the same treatment as they would have received if they had decided not to participate. Therefore, there is neither an additional risk nor a direct benefit related to the participation in the study.

9. Adverse Events and Safety Monitoring

AEs are defined as any untoward medical occurrences, unintended disease or injury or any untoward clinical signs (including abnormal laboratory findings) in patients, users or other persons whether or not related to the investigational medical device.[56] According to the primary and secondary endpoints of this study, the documentation of adverse events will concern all serious adverse events and adverse events related to the initial study procedure or the study device, regardless of the severity throughout 36 months.

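### The adverse event definitions in SAP 2.3.1.2 and Protocol 3.3.1, read literally, exclude unrelated SAEs from the primary safety endpoint, while Protocol section 9 includes them

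*SAP*

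**What the plan says.** SAP 2.3.1.2 defines the primary safety endpoint. It describes an AE as an untoward occurrence "in patients, users or other persons related to the investigational medical device or procedure". It adds: "For this study, only device or procedure related adverse events need to be reported". It then builds the SAE on the AE: "A serious adverse event is an adverse event that led to death or lead to serious deterioration in the health of the subject".

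Protocol 3.3.1 has the same structure. It says "For this study, only device or procedure related AEs need to be reported", and an SAE is "An AE that led to death or lead to serious deterioration in the health of the subject".

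The opening paragraph of Protocol section 9, directly after 8.4, takes the opposite position. AEs there are occurrences "in patients, users or other persons whether or not related to the investigational medical device". It continues: "According to the primary and secondary endpoints of this study, the documentation of adverse events will concern all serious adverse events", together with AEs of any severity related to the device or the initial procedure.

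SAP 5.4 and Protocol 10.3.4 name the endpoint and say that counts are tabulated at 12 months. The visible text gives no test or threshold for safety.

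**The concern.** The primary safety analysis is a count, so the definition of a countable event largely determines the result. Someone programming the Primary Safety at 12 Months table would naturally turn to the SAP's own definition, which is the narrow one. Someone working from Protocol section 9 would include every SAE. Both would be following current text, and they could report different numbers for a primary endpoint. There is also a question of recording: an unrelated SAE that a site never enters cannot be restored at the analysis stage.

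**Working it through.** No figure in the plan rests on this definition, so the check is a comparison of texts followed by a short identity.

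**Step 1. The narrow chain.** In SAP 2.3.1.2 and Protocol 3.3.1, (a) an AE must be related, (b) only related AEs need reporting, and (c) an SAE is an AE with a serious outcome. From (a) and (c), an SAE must be related. Neither section exempts SAEs from (b).

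**Step 2. The wide rule.** Protocol section 9 removes the relatedness condition from the AE definition and asks for all SAEs plus related AEs. It says that it does so because of the study's endpoints.

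**Step 3. Which rule the other text fits.**

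| Place | Content | Fits |
|---|---|---|
| Protocol 3.2, SAP 2.2 | Data for the primary endpoint analysis include "evaluations, SAEs, device, and procedure related AEs" | Wide: SAEs are a separate item |
| Protocol 2.2, SAP 2.1.2 | Secondary objectives list SAEs apart from related AEs | Wide |
| Protocol 5.1, Table 4 | One row names SAEs and, separately, related AEs | Wide |
| Protocol 5.7.1 | Sites record both, and are sent to section 9 for details | Wide |
| Protocol 9.1.1 | A Not Related category exists | Wide |
| SAP 8.1 | One table of all SAEs and another of related SAEs | Wide: under the narrow chain the two would be identical |
| Protocol 3.3.2 and 10.3.4, SAP 5.4 | Endpoint sentences in which the relatedness phrase can govern one term or both | Ambiguous, but naming SAEs would be redundant under the narrow chain |
| Protocol 5.7, introductory list | Names related AEs and omits SAEs | Narrow, largely repaired by 5.7.1 |

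Two passages that might seem to help do not separate the rules. A non-serious Type V endoleak, classed as of unknown relationship in Protocol 9.1.3, is outside both rules. The cardiac arrest example in Protocol 9.1.4 could be procedure related.

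**Step 4. The gap between the rules.** Count events.

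- Wide count = all SAEs + related non-serious AEs
- Narrow count = related SAEs + related non-serious AEs
- Wide − Narrow = all SAEs − related SAEs = SAEs judged Not Related + SAEs of Unknown Relationship

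Each such SAE changes the event count by 1. With none, the counts coincide. The documents give no rate, so the identity cannot be turned into a number.

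**Step 5. What can be recovered.** If sites record under section 9, both counts can be obtained from the SAE tables in SAP 8.1 and the listing of all AEs in SAP 8.2, and only the choice for the primary table is open. If a site recorded under 3.3.1 literally, its unrelated SAEs would not be entered as AEs. Deaths, amputations and re-interventions would still appear in their own SAP 8.2 listings, and SAP 8.1 tabulates discontinuation for bypass, amputation above the metatarsal and death. Other unrelated SAEs, such as a non-fatal hospitalisation, might appear nowhere.

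**The case against.** The strongest reply is that the protocol largely resolves the conflict. Section 5.7.1 names SAEs separately and directs sites to section 9, Table 4 does not tie SAEs to relatedness, and entered data are monitored against source (Protocol 6.2.2 and 7.2). The first sentence of SAP 2.3.1.2 would itself be redundant if every SAE had to be related. On this view only a wording slip remains.

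Much of that stands. It establishes the likely intent and makes literal use of 3.3.1 by a site less probable. It does not remove the narrow definition from the SAP section that defines the endpoint, and no SAP passage says which rule the primary table follows. Monitoring helps only in part, because finding an unrecorded event depends on which rule the monitor applies.

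A reader might go further and infer that unrelated SAEs have been lost, or that the safety result will be understated by some percentage. The documents support neither. Nothing shows that a site used the narrow rule, and any percentage would rest on a rate that the documents do not contain. Nor is it right that every unrelated SAE would vanish from the outputs, given the separate listings for deaths, amputations and re-interventions.

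**Conclusion.** The conflict is real, lies in current text and concerns a primary endpoint. The wording to correct is in SAP 2.3.1.2 and Protocol 3.3.1, because section 9 and most of the supporting text agree with each other. The main consequence is an undetermined rule for the 12-month primary safety table. Incomplete recording at a site is a secondary risk without evidence that it occurred.

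The size is unknown: it is the number of SAEs judged Not Related or of Unknown Relationship, possibly zero. This assumes that an Unknown Relationship event does not count as related under the narrow definition, which the text implies but does not state. Confidence is high for the contradiction. There is no basis for claiming lost data or a changed conclusion.

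**What to change.** 1. In SAP 2.3.1.2 and Protocol 3.3.1, replace the AE definition and the sentence limiting reporting to related events with the section 9 wording. All SAEs are then reported whatever their relationship, and the relatedness restriction applies only to non-serious AEs. Add one exception: all endoleaks are reported, as Protocol 9.1.3 already requires. Without it the new wording would contradict 9.1.3.
2. In SAP 5.4, state that the 12-month primary safety table counts all SAEs regardless of relationship plus non-serious AEs related to the device or procedure. Show non-serious events of Unknown Relationship in a separate row, so that the count can be read with and without them.
3. Add SAEs to the introductory list in Protocol 5.7 and remind sites that all SAEs are recorded.

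The cost is low. Protocol 9.1.3 already collects relationship and seriousness for each event, and SAP 8.1 already plans the all-SAE and related-SAE tables. What remains is a wording amendment, submitted to CCTIRS and CNIL under Protocol 6.5, and a chart re-check only at a site found to have applied the narrow rule.
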